**Project Title: DIABETES AUTOIMMUNITY STUDY IN THE YOUNG**  
**Principal Investigator: [name]**  
**Version date: 5/6/21**

### **I. Hypotheses and Specific Aims:**

The incidence of type 1 diabetes (T1D) has quadrupled over the past 40 years. T1D now affects 1.4 million people in the U.S.; at least as many asymptomatic persons express multiple islet autoantibodies and will develop T1D in the next 10 years. The Diabetes Autoimmunity in the Young (DAISY) prospective cohort has already provided a wealth of clues concerning the natural history and etiology of childhood T1D. With the cohort entering adulthood we are proposing to explore the natural history of autoimmune diabetes phenotypes in young adults. While it is generally accepted that the chronic autoimmune destruction of pancreatic  $\beta$ -cells leading to T1D is triggered by an interaction of environmental factor(s) with a relatively common genetic background, the specific cause remains elusive. We also poorly understand the determinants of prolonged relapsing-remitting course of islet autoimmunity (IA) leading to diabetes. In this application, we propose to shift the paradigm from evaluating a handful of candidate triggers or promoters at a time, to predictive modeling across an array of biomedical domains and serial measurements spanning up to 25 years of life. A major focus of this application is to expand our understanding of changes in the human proteome associated with triggering of IA and progression to diabetes. Previously collected environmental exposure and immune markers data will be combined with genetic, epigenetic, transcriptomic, and metabolomic profiles of DAISY participants obtained through independent funding. We will fully interrogate the complex interplay of IA/T1D biomarkers by combining of Bayesian integration with the power of individualized algorithms to inform new approaches to prevention.

- **Specific Aim 1. Determine the natural history of islet autoimmunity and to explore the heterogeneity of diabetes and other autoimmune phenotypes in young adults through follow-up of the existing cohort for 5 more years.**
- We will follow already established cohort of youth at high risk of T1D and other autoimmune diseases (current n=1149, median age 17.2 y, IQR 13.5-20.2 y). We will estimate overall burden of pre-clinical and clinical T1D, celiac, thyroid, adrenal, rheumatic and parietal autoimmune disease in Colorado by age 25. This will inform future screening and prevention programs. We will further explore the apparent heterogeneity of IA and its implications for adult-onset diabetes. Selected hypotheses include:
  - Hypothesis 1.1: Persistent IA triggered after the age of 6 y results in T1D diagnosis in early adulthood
  - Hypothesis 1.2: Transient childhood IA does not increase the risk of diabetes in early adulthood
  - Hypothesis 1.3: Sedentary life-style and insulin resistance predict faster progression from persistent IA to T1D
- **Specific Aim 2. Validate candidate proteomic biomarkers of IA and T1D, in a nested-case study of 213 youth with persistent IA and 213 controls.**

- So far, none of the ‘omics biomarkers reported to predict progression from IA to T1D have been confirmed by independent studies. Using targeted proteomics we will validate candidate peptides/proteins reported from several discovery studies. Selected hypotheses:
- Hypothesis 2.1: A reproducible set of proteomic biomarkers will predict development of IA independently of demographic factors and HLA class II genotypes.
- Hypothesis 2.2: A reproducible set of proteomic biomarkers will predict the rate of progression from IA to T1D independently of demographic factors, HLA class II genotypes.
- **Specific Aim 3. Develop an integrated comprehensive model of the relapsing-remitting process leading to T1D in youth using prospectively collected DAISY ‘omics data.**
- Integrative Bayesian modeling, based on a small set of disparate features e.g., gene variants, proteins, or metabolites, will be used to generate individualized prediction algorithms in IA progressors vs. non-progressors to identify potential pathways. Selected hypotheses:
- Hypothesis 3.1: A limited number of features derived from high-resolution ‘omics data can reliably predict development of IA on an individual basis
- Hypothesis 3.2: A limited number of features and time-points derived from high-resolution ‘omics data can reliably predict the rate of progression from IA to T1D on an individual basis
- 
- The proposed studies are important to reach our overarching goals: to find the environmental causes of T1D, develop primary prevention, and inform public health screening for several autoimmune disorders in children and adolescents. We will continue to make every effort to share DAISY resources with multiple investigators studying T1D and other autoimmune diseases through an open-source database/ repository.

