### **Progression from Islet Autoimmunity (IA) to T1D**

Hypothesis 1.1: Persistent IA triggered after age 6 y results in T1D diagnosis in early adulthood

Hypothesis 1.2: Transient childhood IA does not increase the risk of diabetes in early adulthood

As of 10/2015, 94 children participating in DAISY follow-up have developed T1D. All but one had expressed IA prior to or at diagnosis. Over 70% of children expressing two or more autoantibodies progressed to T1D in 10 years since seroconversion, compared to 15% of those with one autoantibody. There was little difference in progression by family history of T1D or presence of the HLA-DR3/4,DQB1\*0302 genotype. PTPN22 and UBASH3A and INS predicted diabetes, controlling for family history of T1D and presence of HLA-DR3/4-DQB1\*0302 genotype. In general population children, risk alleles at these 5 genetic markers conferred combined HR of 13 for IA and >40 for T1D. INS, UBASH3A, and IFIH1 were significantly associated with progression from IA to T1D, while PTPN22 and IL27 showed a borderline association. Age of appearance of first autoantibody and mean IAA levels during the follow-up were major determinants of the age at diagnosis. In contrast, levels of GAA or IA-2A did not predict time to progression to diabetes.

***New assays for insulin/proinsulin and GAD autoantibody detection:*** Serial serum samples from DAISY participants followed from birth who progressed to T1D were essential in development of novel assays for insulin/proinsulin autoantibodies (IAA), GADA and TGA. These nonradioactive electrochemiluminescence-based assays have been developed on a platform from MesoScale Discovery (MSD). The ECL-IAA assay detects onset of IA earlier than any current standard radioassays in 24% of children, thus defining more precisely the onset of IA and timing of potential triggering events. Both ECL-IAA and ECL-GADA assays are more specific for high-affinity autoantibodies that predict progression to T1D. Next, the individual ECL assays were adapted to measure four antibodies in a single well using a small blood volume (6ul). Using a MSD QuickPlex 4-Spot plate or U-Plex plate, we successfully combined ECL-IAA, GADA and IA-2A with transglutaminase autoantibodies (ECL-TGA) in a single well of a 96 well plate. The multiplex ECL

[figure not shown]

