**Risk of T1D in subjects with a single islet autoantibody**

Nearly a half of children with IA persistently express a single autoantibody: 46% in DAISY, 45% in combined DAISY, BABYDIAB and DIPP cohorts and 40% in TEDDY. Fewer than 15% of these children progress to diabetes in 10 years.

Those who do progress, typically have high-affinity islet autoantibodies. The ECL-based IAA and GADA assays detect only high-affinity autoantibodies and efficiently classify single islet autoantibodies into high-risk vs. no risk (**Figure 5**).

**Figure 5: High rate of progression to T1D among subjects with a single persistent islet autoantibody by radioassay, confirmed as high-affinity by ECL; 29% and 35% risk of T1D in 5 and 10 years**

**Laboratory** Serum samples are stored at -70°C prior to testing. All measurements are performed on coded samples with blinded duplicate testing of all positive and 5% of negative samples. Islet autoantibodies are measured, in the laboratory of [name] (the reference laboratory for TrialNet, TEDDY and T1DGC). In the Diabetes Autoantibody Standardization Program (DASP) workshop, sensitivity and specificity were, respectively, 72% and 99% for GAA, 62% and 99% for IA-2A, 62% and 99% for ZnT8A, and 48% and 100% for IAA. Transplacental autoantibodies are excluded. TG IgA autoantibodies are measured at all visits (by R01 DK-50979). TPO (with TSH and T4, if positive), autoantibodies to 21OH (adrenal) and to cyclic citrullinated peptide (rheumatoid arthritis) - will be re-measured only once at age 20 or the end of the follow-up. Standard methods will be used to measure: HbA1c, blood glucose, fasting total-, HDL-cholesterol and triglycerides. Adiponectin, insulin and C-peptide will be measured using radioimmunoassays.

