**SIGNIFICANCE:** Machine learning algorithms are currently used for predictive modeling across an array of biomedical domains. Some of the most popular include Random Forests (RF) and Support Vector Machines (SVM); however, traditional algorithms such as Naïve Bayes (NB), Linear Discriminant Analysis (LDA), and K-Nearest neighbors are still often used. These algorithms have various levels of success when faced with qualitative variables and missing data. [name] has developed a methodology that uses the benefits of simple naïve Bayesian integration with the power of individualized algorithms best suited to specific datasets often referred to as meta-learning or ensemble methods. The probability of the outcome of an individual is the combined evidence from multiple datasets, each modeled independently. This approach allows predictors from different algorithms to be utilized in another machine learning algorithm, NB in this case, to relate the datasets to one another in the context of a common outcome. Bayesian integration ensemble feature finder (BIFF) uses a statistical optimization algorithm known as simulated annealing. A major issue with feature selection algorithms is they return a single solution via greedy optimization of a defined criteria, such as the area under a ROC curve. However, this is only one of likely many potential solutions, especially when the feature space is large and disparate. The BIFF approach allows the algorithm to move out of local minima by updating the solution at each iteration, based on the current feature state and sampling in proportion to including or excluding the variable of interest. Integrative Bayesian modeling, based on a set of disparate features e.g., gene variants, proteins, or metabolites, will be used to generate individualized prediction algorithms in IA progressors vs. non-progressors. The DAISY population with its rich longitudinal data set is ideal for the development of statistical machine learning models that can explore individualized and subgroup predictors of IA development and progression from IA to T1D. In addition, pairing clustering with selected features will offer a new approach to evaluate features in the context of pathways. The major advantage of this study is the prospective characterization of autoimmunity over a prolonged period of time, with high-frequency of repeat measurements of biomarkers. This approach will improve prediction of T1D and may identify new targets for prevention.

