**Figure 7: Lower levels of vitamin C at T1 (infancy) predict development of IA.**

Proteins/peptides Relative abundance of 1001 serum proteins measured by aptamers (Somalogic, Boulder, CO) and 49 peptides (representing 24 proteins) measured by LC-MRM/MS in DAISY1 study were included.

[figure not shown]
We first compared BIFF to standard Recursive Feature Elimination (RFE) approaches in combination with cross-validation (CV). RFE is a method using extensively in biology in combination with various machine learning algorithms, such as LDA and SVMs. RFE is readily available in most statistical programming languages and is simple to implement. It is a greedy algorithm that sequentially eliminates features to maximize AUC.

In respect to the hypotheses of interest, comparing the early time points, T2 and T1, for development of IA, the control group was compared to the combined group of subjects with IA+ and T1D (Hypothesis 3.1); for progression to T1D (Hypothesis 3.2), T3 and T4 were compared between the IA+ and T1D groups.

Figures 8A and B show the results of these comparisons, respectively, as a ROC curve for the SA approach at a 50% frequency selection. For comparison purposes we also evaluated these two comparisons with standard repeated recursive feature elimination (RFE) and selected features similarly based on percentage of times the features were selected at either 25% or 50% frequency, as well as all features. There is a clear advantage to the integrated feature selection approach of BIFF (SA\_50). Features selected are quantified based on the percentage of times selected, and ordered based on this percentage. This allows the features to be evaluated in the context of the integrated model to determine the key biomarker panel in lieu of specific datasets.

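### Aim 3 promises improved prediction of T1D, but Hypotheses 3.1 and 3.2 set no reference model of known predictors against which a gain from the 'omics panel could be shown

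*Protocol*

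**What the plan says.** Hypothesis 3.2 (Section I, repeated under Specific Aim 3 in the Research Plan) holds that a limited number of features and time points from 'omics "data can reliably predict the rate of progression from IA to T1D on an individual basis". Hypothesis 3.1 says the same of developing islet autoimmunity (IA). Neither gives a performance threshold, a comparator or a requirement of independence from other predictors. Hypothesis 2.2 does: its proteomic markers must predict progression "independently of demographic factors, HLA class II genotypes", and Hypothesis 2.1 has a matching clause.

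The Significance paragraph of Specific Aim 3 goes further than Hypotheses 3.1 and 3.2: "This approach will improve prediction of T1D and may identify new targets for prevention".

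The only performance comparison described for Aim 3 is in its Preliminary Evaluation, run on the DAISY1 set (25 T1D, 20 IA-positive, 25 controls): "We first compared BIFF to standard Recursive Feature Elimination (RFE) approaches in combination with cross-validation (CV"). The comparators were recursive feature elimination (RFE) at 25% or 50% selection frequency and the full feature set. Demographics, family history, HLA-DR,DQ, SNPs and immune markers were among the domains compared there, so known predictors can enter as features. No model made of them alone is described.

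**The concern.** An improvement needs a baseline. Comparing the Bayesian integration algorithm (BIFF) with RFE shows which algorithm selects better from the same features. It does not show whether the 'omics layer adds to what the study already knows about a child.

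The protocol itself reports strong existing predictors. For progression these are autoantibody number, autoantibody affinity, age at first autoantibody and early dysglycaemia. For development of IA they are HLA and family history. Among children with the DR3/4 genotype, 51% of siblings develop IA by age 15 against 18% of children without an affected first-degree relative (HR 3.8). The Aim 2 and 3 controls are frequency matched on age, sex and ethnicity only, so HLA and family history remain free to separate cases from controls.

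The preliminary results show how this could mislead. In Table 5 glucose is selected in 100% of runs for progression and mannose in 99%, and the text reads the metabolic features as reflecting dysglycaemia and lipolysis. One of the two time points used is the last sample before diagnosis, and HbA1c and glucose are already measured in autoantibody-positive children. A panel that largely re-expresses glycaemia or antibody status could satisfy Hypothesis 3.2 and then be cited as improved prediction.

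**Working it through.** The document text gives no AUC or power figure for Aim 3 (the ROC curves of Figure 8 are not shown), so there is no stated figure to reproduce. The check asks what discrimination autoantibody number alone would have for Hypothesis 3.2.

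**Inputs**
- Single-antibody share, 0.46, so multiple 0.54: "Nearly a half of children with IA persistently express a single autoantibody: 46% in DAISY".
- Ten-year progression with two or more antibodies, taken as 0.70: "Over 70% of children expressing two or more autoantibodies progressed to T1D in 10 years since seroconversion".
- Ten-year progression with one antibody, taken as 0.15: "compared to 15% of those with one autoantibody". Elsewhere this is an upper bound: "Fewer than 15% of these children progress to diabetes in 10 years".
- Case set (Specific Aim 2, Approach): 213 cases, of whom 89 have T1D, 61 have two or more antibodies or one high-affinity antibody, and 63 have one low-affinity antibody. Non-T1D: 61 + 63 = 124.
- Multiple antibodies at first presentation (Section III): 32% of 143 early-onset and 15% of 65 late-onset.

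**Formula.** For one binary marker, AUC = (sensitivity + specificity) / 2.

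**Step 1: the protocol's rates**
- Progressors: 0.54 × 0.70 = 0.378 multiple; 0.46 × 0.15 = 0.069 single; total 0.447.
- Non-progressors: 0.54 × 0.30 = 0.162 multiple; 0.46 × 0.85 = 0.391 single; total 0.553.
- Sensitivity = 0.378 / 0.447 = 0.846. Specificity = 0.391 / 0.553 = 0.707.
- AUC = (0.846 + 0.707) / 2 = 0.776.
- With 40–46% single and 10–15% progression in singles, the AUC runs from 0.764 to 0.805. Allowing 75% for multiples as well raises the top to 0.826. The 10% and 75% are assumptions.
- Plausibility: the rates imply 44.7% progressors, against 89/213 = 41.8% in the case set and 94/222 = 42.3% in the cohort to date.

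**Step 2: the 213-case set**
- By number, assuming 46% single and 15% of singles progressing: 0.46 × 213 = 98.0 singles, of whom 14.7 progress. Sensitivity = (89 − 14.7) / 89 = 0.835; specificity = (98.0 − 14.7) / 124 = 0.672; AUC = 0.753.
- By number or affinity: specificity = 63 / 124 = 0.508. The 89 T1D cases are not classified by antibody, so sensitivity is assumed: 0.846 gives AUC 0.677 and 1.00 gives 0.754.
- Together: about 0.68 to 0.75.

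**Step 3: first presentation only**
- Multiple at presentation: (0.32 × 143 + 0.15 × 65) / 208 = 55.5 / 208 = 0.267.
- With 44.7% progressing overall and an assumed 70% risk in those presenting with multiple antibodies: sensitivity 0.418, specificity 0.855, AUC 0.637.
- With an assumed 90% risk: sensitivity 0.537, specificity 0.952, AUC 0.745.
- Together: about 0.64 to 0.75.

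**The case against.** The strongest reply is that this is an omission of the kind a statistical analysis plan would fill. Aim 3 sets out to develop a model and find pathways, and its hypotheses claim neither independence nor increment. Part of that stands: a separate plan may name a base model, and Section F, which covers Aims 1 and 2, states no wrong rule for Aim 3. It does not dispose of the mismatch within the protocol, which asserts improvement while wording its hypotheses so that improvement need not be shown.

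Four stronger readings are tempting, and the documents do not support them.
- *The panel will be judged only against other feature-selection runs.* The RFE comparison is a completed proof of principle on DAISY1. It is not stated as the criterion for the planned analysis of 213 cases and 213 controls, for which no performance comparison is given.
- *Known predictors are ignored.* They are eligible features, and the selection frequencies reveal them when they dominate. In addition, the Aim 1 joint latent class model predicts time from IA to T1D from age, HLA, family history, glucose and additional autoantibodies, and summarises its dynamic accuracy. That is close to a reference model, but nothing links it to Aim 3.
- *0.78 is the benchmark for the whole aim.* It cannot apply to Hypothesis 3.1, where IA is itself the outcome. The 46% describes persistent single-antibody status over follow-up, so 0.78 suits late samples better than those taken just after IA begins. It also treats ten-year progression as binary, whereas Hypothesis 3.2 concerns rate.
- *A panel with the same AUC adds nothing.* Two predictors with equal AUC can carry different information, and a weakly correlated panel would improve a combined model.

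**Conclusion.** The point holds in a limited form. The claim of improved prediction is not tested by Hypotheses 3.1 and 3.2 as worded, because no model of known predictors alone serves as the reference. For Hypothesis 3.2 the comparison a panel would need to beat is not trivial: an AUC of about 0.78 from the protocol's own rates, with the lower values from Steps 2 and 3 for the case set and for first presentation. These figures rest on reading the over-70% and under-15% rates at 70% and 15%, on the assumed sensitivities and risks shown, and on a binary ten-year outcome. No magnitude can be derived for Hypothesis 3.1. A panel AUC in these ranges would leave open whether the 'omics contribute. The study can proceed, but the wording should be changed before the result is interpreted.

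**What to change.** State that, within the same outer cross-validation folds, a base model and a base-plus-'omics model will be fitted, and report the paired difference in discrimination with a 95% CI.
- **Hypothesis 3.2:** use a time-to-event measure (C-index or time-dependent AUC), since the hypothesis concerns rate. Base variables: autoantibody number and affinity, age at seroconversion, HLA-DR,DQ, family history, and HbA1c/glucose at the same visit.
- **Hypothesis 3.1:** base variables HLA-DR,DQ and family history. Age, sex and ethnicity enter as adjusters only, because controls are frequency matched on them and they can discriminate little by design.
- **Claim:** state improved prediction only if the lower confidence limit for the gain is above zero. Otherwise report the panel's accuracy without that claim.

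The cost is one extra model per outcome and some wording. The protocol describes the base variables as collected, but it does not give antibody affinity for the 89 T1D cases, so its availability should be confirmed. The downside is that the reportable gain will be smaller than the raw AUC.

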## II. Background and Significance:

The incidence of type 1 diabetes (T1D) has quadrupled over the past 40 years, now affecting 1.4 million people in the U.S. At least as many asymptomatic persons express multiple islet autoantibodies and will develop T1D in the next 10 years. The Diabetes Autoimmunity in the Young (DAISY) prospective cohort is now entering adulthood so we propose to explore the natural history of autoimmune diabetes phenotypes in young adults. While it is generally accepted that the chronic autoimmune destruction of pancreatic  $\beta$ -cells leading to T1D is triggered by an interaction of environmental factor(s) with a relatively common genetic background, the specific cause remains elusive. We also poorly understand the determinants of prolonged relapsing-remitting course of islet autoimmunity (IA) leading to T1D. We propose to shift the paradigm from evaluating a handful of candidate triggers at a time, to predictive modeling across an array of biomedical domains and serial measurements spanning up to 25 years of life. Our focus is to expand our understanding of changes in human proteome associated with development of IA and T1D. Combining environmental exposures and immune marker data with genetic, epigenetic, transcriptomic, and metabolomic profiles will allow us to interrogate the complex interplay of IA/T1D biomarkers utilizing Bayesian integration with the power of individualized algorithms to inform new approaches to prevention. 1) The established cohort of youth at high risk of T1D and other autoimmune diseases (n=1149, median age 17.2 y, IQR 13.5-20.2 y) will be followed to estimate overall burden of T1D, celiac, thyroid and other autoimmune disease, by age 25. We will further explore the apparent heterogeneity of islet autoimmunity and its implications for adult-onset diabetes. 2) Targeted proteomics will validate candidate protein biomarkers of IA and T1D reported from discovery studies. 3) Integrative Bayesian modeling, based on a small set of disparate features (gene variants, proteins, or metabolites) will be used to generate individualized prediction algorithms in IA progressors vs. non-progressors and to identify potential pathways. The proposed studies are important to reach our overarching goals: to find the environmental causes of T1D, develop primary prevention, and inform public health screening for several autoimmune disorders

in children and adolescents. We will continue to make every effort to share DAISY resources with multiple investigators studying T1D and other autoimmune diseases through an open-source database/ repository. 6

